The association of HIV-1 -specific CTL with non-progressive disease in HIV-1 infected persons, as well as the increased frequency of certain HLA class I alleles in HEPS populations, has led several groups to look for HLA class I restricted, HIV-1 -specific CTL in these groups(17-24). HIV-1 -specific CTL have now been described in the peripheral blood of HEPS (16). Studies by several investigators have shown that HIV-1 -specific CD8⁺ T cells can be detected in the peripheral blood of 30-60% of HEPS tested. These CD8⁺ responses have been measured both in conventional CTL lysis assays (20) as well as IFN- γ ELISPOT assays (21). Responses to multiple HIV-1 antigens were detected including env, gag, pol and nef. Interestingly, HIV-1 -specific CTL have recently been demonstrated in the genital tract, the

likely site of viral exposure, in a subset of a HEPS cohort in Nairobi (21). It has been hypothesized that a primed CTL response at the site of exposure would be more relevant in protection against incident HIV-1 infection than in blood, where HEPS CTL responses have been previously described (21). These CD8⁺ cells were most likely intraepithelial memory T lymphocytes generated in secondary lymphoid organs that localize to epithelial sites upon reexposure to antigen (25). Overall, these responses (both mucosal and peripheral) tended to be lower and not as durable as those seen in seropositive individuals. Nonetheless, the detection of HIV-1 -specific CTL in the genital tract of these HEPS suggests that these responses may be important in mediating protective immunity against heterosexual HIV-1 acquisition.

Resistance to infection with HIV-1 based on a noncytolytic CD8⁺ T cell-mediated mechanism has also been reported. Stranford et al described a CD8⁺-mediated, noncytolytic anti-HIV-1 activity that was seen in the vast majority of individuals most recently exposed to the virus (within 1 year), and was potent enough to inhibit *in vitro* infection of subject's PBMC (26). Paxton et al, showed that resistance to infection of CD4⁺ lymphocytes from HEPS was associated with the activity of C-C chemokines such as RANTES, MIP1 α , and MIP-1 β (27-29). Other HIV-1 -specific immune responses have also been observed in HEPS cohorts such as IgA in mucosa (30) (31;32)and serum (33), and serum antibodies to HLA molecules (34;35) and CD4 (36). The contribution of these mechanisms to resistance to HIV-1 infection remains unclear.

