2.0 STUDY OBJECTIVES AND DESIGN

2.1 Primary Objectives

- To determine if the detection of an HIV-1 -specific immune response in exposed uninfected individuals correlates with risk of subsequent HIV-1 infection.
- To determine if immunologic genetic characteristics of exposed uninfected individuals correlates with risk of subsequent HIV-1 infection.

2.2 Secondary Objectives:

- To determine if the detection of an HIV-1 -specific immune response in exposed uninfected individuals correlates with the HIV-1 viral set point in individuals that subsequently become HIV-1 infected.
- To compare the epitope specificity of the HIV-1 -specific immune response of exposed-uninfected individuals with that of their recently infected partners.
- To assess the feasibility of establishing a prospective cohort of recently infected individuals and their primary sexual partners for participation in HPTN HIV-1 prevention trials of discordant couples.

2.3 Study Design:

This is a prospective cohort study to be conducted at NARI. NARI will implement the study in accordance with this protocol, however additional studies and collaborations may be incorporated into this study with approval from the Executive Committee. NARI will document study data using standard data collection forms to be submitted to the HPTN Statistical and Data Management Center (SDMC).

An estimated 10-15 individuals/year who qualify as HIV-1 -exposed uninfected are expected to be enrolled in this study. To maximize efficiency and to utilize established systems for screening and follow-up, individuals who themselves are HIV-1 negative, but who have recently infected partners will be recruited from the ongoing 034 HPTN trial. Enrollment will be offered to all participants in HPTN protocols who fulfill the enrollment inclusion/exclusion criteria. Individuals will necessarily have had a previously documented negative HIV-1 test that will be confirmed by HIV-1 RNA PCR. Appendix A (Table 1) reflects the clinical and laboratory specimens that will be collected at each visit. In this protocol, only samples from exposed-uninfected individuals will be collected. Samples from seropositive and seronegative individuals enrolled in the 034AHPTN Early HIV-1 Infection Study Laboroatory Sub-study will serve as comparative controls for the assays performed in the exposed-uninfected study.

3.0 Study Population:

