6.3 Statistical Considerations and Sample Size Calculations

Based upon assumptions outlined below for each of the two primary objectives, the target samples size for this study is a minimum of 20 subjects who are HIV-1 -exposed uninfected individuals with recently infected partners. For both primary objectives, frequency of HIV-1 infection will be an outcome measure. Patients will be divided into an infected and uninfected

cohort and compared with respect to the presence or absence of any prior detectable immune response as measured by Elispot.

6.3.1 Primary Objectives (a). Gag-specific ELISPOT Response vs. subsequent HIV-1 Infection.

For the purposes of comparing ELISPOT response to incidence of infections, gag-specific ELISPOT responses will be scored as positive or negative. As outlined in Appendix C, all experiments will be performed in duplicate wells. The IFN- γ -expressing spots will be calculated as the number of spots per 10⁵ stimulated PBMCs. Results will be expressed as net peptide-specific IFN- γ spots / 10⁵ PBMC. A positive peptide-specific response (responders) will be defined as a mean of greater than 5 spots above the mean spots of the mock-stimulated PBMC. Study participants will be expected to have multiple ELISPOT assays within the first 12 months of follow-up (See Appendix A). For the purpose of the sample size calculation, our initial analysis will compare HIV-infection with a positive response to any gag peptide, at any time point within 12 months since enrollment. Separate and similar analyses will be performed for recognition of HIV-1 subtype B gag and non-B gag peptides. Assuming a 20% seroconversion rate among the exposed uninfected cohort resulting in 20 acutely infected patients, we would have 80% power to detect at least a 25% difference in the proportion of individuals who elicit a gag immune response between the two groups (infected and uninfected).

Difference in proportion of patients with	Total sample size (unequal arms assuming
gag response	20% seroconversion rate)
20%	238
25%	138
30%	86

6.3.2 Correlation of HLA allelic expression with risk of subsequent infection.

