The proportion of individuals with certain HLA Class I alleles will be compared between infected and uninfected individuals. Using HLA A2 as an example (known to exhibit good immune response to gag), we posit that a higher percentage of this allele will be found in the uninfected cohort. Using a similar calculation to 6.3.1, we will have 80% power to detect at least a 25% difference in allelic frequency between the two groups.

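### Sub-study 034B claims 80% power for a 25-point difference, but its section 6.3 gives three incompatible sizes (20, 100 and 138), and the size it expects to enrol cannot deliver that power

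*Supplement*

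**What the plan says.** The 034B sub-study has two primary objectives: whether a gag-specific ELISPOT response, and whether HLA class I type, correlates with later HIV-1 infection in exposed uninfected partners.

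- **Target (034B section 6.3).** The "target samples size for this study is a minimum of 20 subjects who are HIV-1 -exposed uninfected individuals with recently infected partners". The section says this target rests on the assumptions that follow for the two primary objectives.
- **Power sentence (034B section 6.3.1).** "Assuming a 20% seroconversion rate among the exposed uninfected cohort resulting in 20 acutely infected patients, we would have 80% power". The effect is given as "80% power to detect at least a 25% difference in the proportion of individuals who elicit a gag immune response between the two groups", meaning infected versus uninfected.
- **Table (034B section 6.3.1).** Under a column headed "Total sample size (unequal arms assuming" a 20% seroconversion rate, totals of 238, 138 and 86 are listed for differences of 20, 25 and 30 points.
- **HLA objective (034B section 6.3.2).** By a similar calculation, "we will have 80% power to detect at least a 25% difference in allelic frequency between the two groups".
- **Accrual (034B section 2.3).** "An estimated 10-15 individuals/year who qualify as HIV-1 -exposed uninfected are expected to be enrolled in this study", at 10 to 15 per year.

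The 034B sample-size section gives no significance level and no response rates. The companion protocol, 034A section 6.3.1, says that sub-study is descriptive, does not expect its 20 to 30 participants to settle the primary endpoint, and assigns its power to a later analysis across HPTN protocols. 034B section 6.3 has no such statement. The May 2004 letter of amendment enlarges the parent cohorts but lists no change to 034B section 6.3.

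**The concern.** One power claim is attached to three different sample sizes. The target of 20 is presented as following from the calculation, the power sentence needs 100, and the table needs 138. They cannot all be right.

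Both primary objectives are presented to ethics committees and readers as tests with 80% power. If about 20 to 30 people enrol, a handful of infections will carry the comparison, and a non-significant result would say almost nothing about immune or HLA protection. A reader relying on the stated power would have no warning of this.

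**Working it through.** **1. Sizes implied by the text (no outside assumption)**

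- Target: 20 participants × 0.20 = 4 infected, 16 uninfected.
- Power sentence: 20 infected ÷ 0.20 = 100 participants, 20 infected and 80 uninfected.
- Table, 25 points: 138 × 0.20 = 27.6, about 28 infected.
- Accrual: 10 to 15 per year gives 20 to 30 people in two years, so 4 to 6 infections at 20%. At that pace 100 people take 100 ÷ 15 = 6.7 to 100 ÷ 10 = 10 years.

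**2. Reproducing the table**

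Assumptions: two-sided alpha 0.05 (034A states p=0.05; 034B states nothing), 80% power, ratio k = 4 uninfected per infected. The response rates are not stated and have to be back-solved. Subscript 1 is the infected group and 2 the uninfected; p̄ = (p₁ + 4p₂)/5 and d = |p₁ − p₂|.

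n₁ = [1.96·√(1.25·p̄(1−p̄)) + 0.8416·√(p₁(1−p₁) + p₂(1−p₂)/4)]² / d², total = 5n₁.

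For 60% versus 85%: p̄ = 0.80. The first term is 1.96·√0.200 = 0.8765 and the second is 0.8416·√0.2719 = 0.4388. So n₁ = 1.3154² / 0.0625 = 27.68, total 138.4.

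| Infected vs uninfected | Difference | Computed total | Table |
|---|---|---|---|
| 60% vs 80% | 20 points | 238.5 | 238 |
| 60% vs 85% | 25 points | 138.4 | 138 |
| 60% vs 90% | 30 points | 84.7 | 86 |

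The mirror image, 40% infected versus 20/15/10% uninfected, gives identical totals. Infected 15/10/5% versus uninfected 35% comes close, at 236/141/89.

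**3. Power at the sizes in the text**

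Power = Φ{[d√n₁ − 1.96·√(1.25·p̄(1−p̄))] / √(p₁(1−p₁) + p₂(1−p₂)/4)}.

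For 60% versus 85%, with 20 infected: (0.25·√20 − 0.8765)/0.5214 = (1.1180 − 0.8765)/0.5214 = 0.463, so power is 67.8%. With 4 infected: (0.5000 − 0.8765)/0.5214 = −0.722, so 23.5%. With 6 infected: (0.6124 − 0.8765)/0.5214 = −0.507, so 30.6%.

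| Participants (infected/uninfected) | Approximate power | Fisher's exact power |
|---|---|---|
| 20 (4/16) | 24% | 14% |
| 30 (6/24) | 31% | 24% |
| 100 (20/80) | 68% | 63% |
| 138 (27.6/110.4; Fisher 28/110) | 80% | 76% |

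With these inputs, 100 participants reach 80% approximate power only at a difference of about 28 points.

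**4. Sensitivity to the unstated rates**

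- With 10% infected versus 35% uninfected, 20/80 gives 62% (Fisher 57%).
- A continuity-corrected fit to the table (65% versus 90%) gives 75% uncorrected power at 20/80 (Fisher 71%).
- Over every 25-point pair on a 5-point grid, in both directions, the highest Fisher power is 26% at 4/16 and 47% at 6/24, both at 75% versus 100%.

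**5. What the expected size can estimate**

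The exact (Clopper-Pearson) 95% limits solve P(X ≥ x | p) = 0.025 and P(X ≤ x | p) = 0.025. For 2 responders among 4 infected they are 7% and 93%; for 3 among 6, 12% and 88%.

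**The case against.** **Back-solved inputs.** The power values depend on response rates and an alpha that 034B does not give. That stands as a caveat on the percentages. At extreme rates (70% versus 95%, for example) 100 participants would exceed 80% power, but such rates would not produce the table's 138. The conflict among 20, 100 and 138 needs no assumed rate, and the low power at 20 or 30 holds across the whole grid.

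**Conditional wording.** The target is a minimum, and section 6.3.1 says what power would be if there were 20 infections. The 034B summary has enrolment running for the HPTN 034 funding period with no fixed end, so 30 is not a ceiling; it is two years at the upper expected rate. This is fair. But section 6.3 ties the target of 20 to these assumptions, section 6.3.2 speaks without condition, and no section of 034B gives a route to 100 or 138.

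**Ancillary status and network framing.** 034B is a laboratory sub-study; the incidence and retention endpoints of HPTN 034 are untouched. Parts of its text look to cohorts across the network, which suggests pooling was in mind. That makes the missing caveat easy to supply, but it does not make the printed power statements true.

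**A stronger reading that fails.** 034B section 1.1 reports that HIV-specific CD8 responses "can be detected in the peripheral blood of 30-60% of HEPS tested", and a reader might infer that the table contradicts this or must be rebuilt on that range. The documents do not support either. Uninfected rates of 34% to 35% come close to reproducing the table and lie inside the range. With 30% to 60% in the uninfected and 25 points less in the infected, the required total runs from 118 to 190, which includes 138. The background figure also covers other antigens and assays, whereas 034B plans a gag-only response at any time within 12 months.

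**Conclusion.** The 80% power statements in 034B sections 6.3.1 and 6.3.2 are not supported by the sizes given there. The text and table disagree (100 against 138) for the same difference at the same seroconversion rate, and the target of 20 is about one seventh of the table's figure (20/138 = 0.14).

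The inconsistency follows from the documents alone. The power figures in the table under step 3 rest on two-sided 0.05, 1:4 allocation and rates of 60% versus 85% (or 40% versus 15%). The weaker statement, that 25 points cannot be tested with anything near 80% power at 20 or 30 participants, rests only on the first two assumptions and Fisher's exact test.

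The table itself is not shown to be wrong; its inputs are simply unstated. Nothing here affects the parent study's sample size.

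**What to change.** 1. Withdraw the 80% power statements in 034B sections 6.3.1 and 6.3.2, or restate them for the number actually expected.
2. State that at about 20 to 30 participants 034B is descriptive, give expected confidence interval widths, and say that powered tests depend on pooling with other HPTN sub-studies, in line with 034A.
3. Make the target, the power sentence and the table agree. If 20 was meant as a number of infections, say so and correct the difference or the total to match.
4. State the alpha, sidedness and assumed response rates behind the table. The choice of rates is the sponsor's; the 30% to 60% background range need not be imposed.

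The cost is a few sentences and one annotated or recalculated table. No visit, assay or eligibility rule changes. The stated power becomes less favourable.

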7.0 Human Subjects Considerations

7.1 IRB Review

This protocol, the proposed informed consent documents and any subsequent modifications will require review and approval by a number of Institutional Review Boards or Ethics Committees, responsible for oversight of the HPTN activities. The activities of this protocol will be covered by an approved HPTN OPRR International Cooperative Project Assurance (ICPA) for each participating site, required for participation in an OPRR-recognized HPTN Cooperative Protocol Research Program (CPRP). It will be the responsibility of participating site investigators to

obtain and document all required approvals for this study. Specifically site participation in this protocol will require documentation of ethical review and approval from the following:

- International HPTUs: Local institutional IRB and IRB of collaborating US institution, when applicable.
- Domestic US HPTUs: Local institutional IRB

7.2 Confidentiality

All local study records will be kept in locked file cabinets in areas with limited access; databases will be secured with password-protected access systems. A coded ID number will identify all study data and specimens only, and records containing participant names or other personal identifiers, such as locator forms and informed consent documents will be stored separately from coded ID records.

7.3 Benefits

Support for HIV-1 Prevention

During the study, the participant will receive the most current information and counseling about how to avoid acquiring or transmitting HIV-1 to partners. Studying immune responses in early HIV-1 infection will provide important knowledge concerning strategies for prevention and vaccine development and evaluation. In light of the high risk of secondary HIV-1 transmission to sexual partners from individuals with recent HIV-1 infection, an important effort will be made to encourage participants to refer their partners for HIV-1 screening and counseling.

Access to Care

The study staff will refer participants for STD treatment and other services as needed according to standard procedures at each site. Each participating HPTU site will be responsible for assuring compliance with their own ethical guidelines for providing the best locally available clinical care to study participants.

7.4 Risks

Health Risks

Study participants may feel discomfort associated with phlebotomy, including pain, bruising and/or in very rare instances, local infection.

Psychosocial Risks

Periodic testing of viral and immunologic indices may increase participant's anxiety level concerning their health and risk of HIV-1 infection.

7.5 Study Discontinuation

The study may be discontinued at anytime by FHI, the HPTN, NIAID or by the government and host-institution of the country in which the study is being conducted.

7.6 Incentives

Participants may be provided a small incentive in the form of a transport allowance and free access to medical services for their participation in this study, as determined by individual sites based on local standards of practice and in accordance with ongoing studies from which the participants will be identified. The details of these incentives will vary from site to site, but must be included in the local IRB approved consent form for each participating HPTU.

8.0 Laboratory Specimens and Biohazard Containment

As the transmission of HIV-1 and other blood-borne pathogens can occur through contact with contaminated needles, blood, and blood products, appropriate blood and secretion precautions will be employed by all personnel when drawing of blood and shipping and handling of all specimens for this study, as currently recommended by the Centers for Disease Control and Prevention.

9.0 Administrative Procedures

9.1 Study Coordination

Close cooperation between the protocols team and site investigators, protocol coordinator, data managers and biostatisticians will be necessary; study progress will be evaluated by the study team on a regular basis via conference calls. The sites will employ a common study specific procedures manual (with site-specific sections as appropriate). This manual will outline procedures for enrollment, follow-up, data and forms processing and other study operations.

A common study laboratory manual will be followed to standardize specimen collection, preparation, testing, processing, and shipping. For laboratory procedures and assays (i.e., cell separations, freezing of samples, flow cytometry, etc.) that can be performed by the local site laboratory, or the HCL. Other assays will be performed at the HCL or in the laboratories of non-HPTN participants/collaborators.

Every effort will be made to provide training and technology transfer to each of the sites to increase their overall capabilities. There will also be a strong commitment to rapid bi-directional exchange of test results and other data to facilitate the collaborative interpretation and timely publication of HPTN findings.

9.2 Study Monitoring

The HCL will conduct site visits to monitor adherence to human subjects and other applicable regulations, adherence to the study protocol and procedure manuals, and the quality of the data collected at the study sites. The study site key investigators will allow the inspection of study documents (e.g., consent forms, process data collection forms, questionnaires) for confirmation of the study data.

9.3 Protocol Compliance

This study will be conducted in full compliance with the protocol. The protocol will not be amended without prior written approval by the Protocol Chairs and DAIDS Medical Officer. Protocol amendments requiring IRB approval must be approved by the IRB prior to implementing any amended procedures.

9.4 Investigator Records

All records must be retained on-site throughout the study's period of performance. The HPTN will provide each site with written instructions for long-term record storage at the completion of the period of performance.

Study records include the following:

- Administrative files, including initiation documents and all reports and correspondence relating to the study.
- Records for each participant, including informed consent forms, locator forms, data collection forms, and source documents

9.5 Use of Information and Publications

The policies that govern specimen ownership, intellectual property rights, and the publication/authorship of research will be derived from the WHO policy document concerning these issues. Virus isolates and any remaining serum/plasma/cell samples, which are not consumed during the specified testing, will be retained in a specimen archive at the local site, the HPTN laboratory, or the NIAID Repository contractor (BRInc.) in Bethesda MD. These samples will be available to any responsible investigator for further studies, pending review of the request by the site that submitted the sample and the HPTN Steering Group or the appropriate oversight committee following HPTN.

Publication of the results of this study will be governed by policies of DAIDS and the HPTN. Any presentation, abstract, or manuscript will be made available by the investigators to DAIDS and the HPTN manuscript review committee for review and comment prior to submission.

APPENDIX A:

Table 1. Scheduled visits for exposed-uninfected individuals

Enrollment Screening

Month	Pre	0	3	6	9	12	15	18	21	24	27	30	33	36
Study Visit	01	02	03	04	05	06	07	08	09	10	11	12	13	14
Patient ID	Х	Х	Х	Х	Х	Х	X	Х	X	Х	X	Х	Х	Х
Physical Exam	Х	Х	Х	Х	Х	Х	X	Х	X	Х	X	Х	Х	Х
Questionnaire	Х	Х	Х	Х	Х	Х	X	Х	X	Х	X	Х	Х	Х
Assays:														
HIV-1 Test ^{1,}	Х	Х	Х	Х	Х	Х	Х	Х	Х	Х	Х	Х	Х	X
HIV-1 RNA PCR ²	[X]													
Sample Storage:														
Plasma ³	Х	Х	Х	Х	Х	Х	X	Х	X	Х	X	Х	Х	X
PBMC		Х	Х	Х	Х	Х	X	Х	X	Х	X	Х	Х	Х
HLA Typing ⁴		Х												
Total blood volume (ml)	10	40	40	40	40	40	40	40	40	40	40	40	40	40
Number of Tubes ⁵	1	4	4	4	4	4	4	4	4	4	4	4	4	4

¹HIV-1 screening will be done at each visit to confirm HIV-1 antibody negativity (screening assay will be site-specific).

²HIV-1 RNA PCR will only be performed upon confirmation of infection. ³Plasma will be stored for detuning assay, VL measurement.

⁴Specimen type to be determined.
⁵Tubes will be 10ml lavender top tubes containing EDTA.

